10.2. Handling of Withdrawals and Dropouts

Withdrawn subjects will be evaluated in the FAS and safety set. Missing values are imputed as mentioned in Section 10.1.

10.3. Data Transformation

For all continuous variables, mean, standard deviation, minimum, maximum, median, 25% quantile and 75% quantile will be calculated per treatment group and overall.

For all categorical variables counts and frequencies of categories will be calculated per treatment group and overall.

10.3.1. Demographic data and other baseline characteristics

10.3.1.1. Age

Age will be calculated as the difference in years (rounded down) between date of birth and the date of the baseline physical examination.

10.3.1.2. Height

A patient's height is either given in cm or inch. Height in inch will be transformed to height in cm and vice versa using the formulae

$$\text{height(cm)} = 2.54 \times \text{height(inch)}$$

$$\text{height(inch)} = 0.3937 \times \text{height(cm)}$$

Hence, height data for each patient will be available in inch as well as in cm.

10.3.1.3. Weight

A patient's weight is either given in kg or lb. Weight in lb will be transformed to weight in kg and vice versa using the formulae

$$\text{weight(kg)} = 0.4536 \times \text{weight(lb)}$$

$$\text{weight(lb)} = 2.2046 \times \text{weight(kg)}$$

Hence, weight data for each patient will be available in lb as well as in kg.

10.3.1.4. Time since injury

The time since injury will be computed as the time in hours between injury and first treatment.

10.3.1.5. *Early grafted wounds*

For each target wound, a binary (yes/no) variable will be computed indicating whether it was early autografted (for definition see Appendix 13.1.1).

For each patient a binary (yes/no) variable will be computed indicating whether the patient had at least one early grafted target wound.

10.3.1.1. *Late grafted wounds*

For each target wound, a binary (yes/no) variable will be computed indicating whether it was late autografted (for definition see Appendix 13.1.1).

For each patient a binary (yes/no) variable will be computed indicating whether the patient had at least one late grafted target wound.

10.3.1.2. *Wounds at least partially found in the anatomical area of the hand*

For each target wound, a binary (yes/no) variable will be computed indicating whether it was at least partially found in the anatomical area of the hand.

For each patient a binary (yes/no) variable will be computed indicating whether the patient had at least one target wound which was at least partially found in the anatomical area of the hand.

10.3.2. Primary Endpoint: Incidence of complete eschar removal in the topical arms

Information on whether complete eschar removal was obtained after the application of NexoBrid or Gel vehicle per target wound will be combined to a single binary variable (yes/no) indicating whether complete eschar removal was achieved for all target wounds of a patient at the end of the eschar removal treatment (after the 2 hrs soaking). The eschar removal treatment may contain one or two topical removal procedures. Complete eschar removal is judged after the last topical procedure in a patient.

Furthermore, for all patients with at least one early grafted target wound (for definition see Appendix 13.1.1), a binary (yes/no) variable will be computed indicating whether complete eschar removal has been achieved in all early grafted wounds of the patient at the end of the eschar removal treatment (after the 2 hrs soaking).

Additionally, for all patients with at least one late grafted target wound (for definition see Appendix 13.1.1), a binary (yes/no) variable will be computed indicating whether complete eschar removal has been achieved in all late grafted wounds of the patient at the end of the eschar removal treatment (after the 2 hrs soaking).

Furthermore, for patients who had at least one target wound that is found, at least partially, in the anatomical area of the hand, a binary (yes/no) variable will be computed, indicating whether complete eschar removal has been achieved in all target wound that are found, at least partially, in the anatomical area of the hand.

10.3.3. Secondary Endpoints

10.3.3.1. Secondary Endpoint: Incidence of surgical excision

For each patient a binary (yes/no) variable will be computed, indicating whether this patient needed surgical excision for eschar removal.

Furthermore, for patients with at least one early grafted target wound, a binary (yes/no) variable will be computed, indicating whether this patient needed surgical excision in an early grafted target wound. Similarly, for patients with at least one late grafted target wound, a binary (yes/no) variable will be computed, indicating whether this patient needed surgical excision in a late grafted target wound.

Additionally, for patients who had at least one target wound that is found, at least partially, in the anatomical area of the hand, a binary (yes/no) variable will be computed, indicating whether this patient needed surgical excision in a target wound that is found, at least partially, in the anatomical area of the hand.

For each patient the number of TWs will be computed and used as an explanatory variable in the analysis of this secondary endpoint.

10.3.3.2. Secondary Endpoint: Time to complete eschar removal

Information about date will be transformed to time in hours from randomization. Time until complete eschar removal will be calculated as the time (in hours) until complete eschar removal has been achieved for a TW. From these times, time to reach complete eschar removal at a patient level, i.e. for all TW's of an individual patient will be calculated. For wounds/patients that do not reach complete eschar removal, their time will be censored at the last non-missing eschar removal assessment (typically the last debridement procedure).

For further analysis, for patients with at least one early grafted target wound, time to complete eschar removal will also be calculated as above, but taking into account only early grafted wounds. Additionally, for patients with at least one late grafted target wound, time to complete eschar removal will also be calculated as above, but taking into account only late grafted wounds.

Additionally, for patients who had at least one target wound that is found, at least partially, in the anatomical area of the hand, time to complete eschar removal will also be calculated as above, but taking into account only target wounds that are found, at least partially, in the anatomical area of the hand.

For an additional analysis, time to complete eschar removal will be computed as above but in hours from injury.

Furthermore, time to complete eschar removal will be computed as above but in hours from ICF.

The patients' age will be categorized into two categories: "younger than 35 years" and "35 years or older". The number 35 years is found to be the median age of the adult population in the previous study MW2004-11-02.

10.3.3.3. Secondary Endpoint: Blood loss

10.3.3.3.1. Blood loss for main analysis

For each patient and each procedure carried out to remove eschar the estimated blood volume (EBV) will be calculated as

$$EBV = 70 \frac{cm^3}{kg} * weight(kg)$$

Furthermore, the total volume of whole blood and packed red blood cells (PRBC) transfused (in milliliters) will be calculated per procedure (transfusions given during the procedure and 4 hours \pm 15 minutes later) and denoted by V_{WB} and V_{PC} in the following.

From these quantities, the blood loss (Actual Blood Loss, ABL) will be calculated using the following formula [25]:

$$ABL = \frac{EBV * (Hb_{before} - Hb_{after})}{(Hb_{before} + Hb_{after})/2} + V_{WB} + \frac{5}{3}V_{PC}$$

The factor of 5/3 is derived from chapter 5 of Transfusion Medicine, 4th Edition [31] and compensates for the fact that equal volumes of whole blood and packed red blood cells are not comparable.

The ABL will be summed over all procedures carried out to remove eschar, with the Hb measured immediately before each procedure and 4 hours after its completion. The amount of blood transfused will be summed over all transfusions carried out during the debridement procedure and 4 hrs later i.e. the before-after periods that are spanned by these Hb measurements.

Additionally, blood loss will be computed considering the whole debridement process as one continuous procedure. For this value, the formula for ABL given above will also be used. However, the ABL will be computed using the Hb measured immediately before the first procedure and 4 hours after completion of the last procedures. The amount of whole blood and packed red blood cells (PRBC) transfused will be calculated as before, but incorporating all such transfusions in the time frame spanned by the Hb measurements used for the calculation (pre first procedure to 4 hrs post last procedure (in which complete debridement was achieved).

Analyses with both blood loss values will be conducted. However, some missing values are expected. The analysis with less missing values will be regarded as more reliable and is therefore considered the main analysis. The other analysis is considered supportive.

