to 30–50% of healthy tissue (mainly dermis), which is essential for the spontaneous epithelialization potential of the wound, may be sacrificed in this procedure, thus usually necessitating autografting. These surgical procedures are traumatic, often long and difficult, require skilled personnel and sophisticated medical resources and are usually accompanied by bleeding [1] [2] [12] [16] [17] and heat loss [18]. The surgically excised raw wound bed should be covered immediately, i.e., in most cases autografted. Thus, the excision is followed by harvesting of autografts from intact, non-injured skin areas, skin graft transplantation, and care of the donor sites in addition to the original burn injury. These surgical procedures are performed under general anesthesia that requires pre- and post-surgical fasting and recovery. In most centers, caution and post surgery intensive care dictate that only a limited percentage of the affected areas (~15%TBSA) will be surgically debrided at one time in order to limit inflicting excessive stress on the patient. Thus, the decision to surgically debride a burn is not taken lightly. Reluctance, hesitation and doubts due to uncertain diagnosis delay the decision to perform surgery, extending the time to start and finish of the debridement from the optimal few hours to several days.

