2.2. Study Objective

1. To demonstrate the efficacy of enzymatic eschar removal with NexoBrid by providing complete eschar removal as compared with Gel Vehicle,
2. To demonstrate the efficacy of enzymatic eschar removal with NexoBrid by providing earlier complete eschar removal, reduction in patients' surgical burden and its related blood loss as compared to SOC,
3. To assess the safety of NexoBrid compared to SOC, including demonstration that treatment with NexoBrid does not cause an unacceptable level of harm on wound closure outcome and long-term outcomes of cosmesis and function

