Physical examination ⁶	X									
Demographic data	X									
Vital Signs	X	X	4h post R	Post S	Post	X				
Pain assessment	X ⁷	X	Post S	Pre and 4h post	X					
Photograph of TWs				Pre & Post		Pre & Post		X	X	

³ This table differs from the corresponding table in the protocol. Minor corrections were performed.

⁴Wound Management will include any, post complete eschar removal additional excisions, Autografts, and donor site data if relevant.

⁵ Data captured will include burn etiology, mechanism of injury, place of injury, treatments prior to admission and general description of the burn wound (anatomical locations and description of the eschar (such as: white, moist, dry, gray, charcoal, etc.), % TBSA assessments and depth

⁶ Physical examination will include height and weight. Height will be taken only once, at screening.
⁷ Photos should be taken after cleansing

Parameter	Screening tests	Baseline within 1 h Pre First treatment session - All arms	Topical arms (NexoBrid or Gel Vehicle): (refer to first and second application). S=Soaking, R=Removal	SOC procedures** (including additional procedures in the topical arms)	Daily assessments	Wound Management & Re-admissions ⁴ , surgical procedures assessment	HD or premature discontinuation visit	Weekly FU*	Long-Term FU (1, 3, 6, 12, 18 & 24 months)*
Clinical assessment of the burn ⁸	X	X	Post S	Post		Post		X	
Local lab - HbA1C, WBC, PhCG	X								
Central lab hematology/ biochemistry tests & Urinalysis	X		4 h Post R	Pre & 4 h Post					
Central lab Hematology							1h pre & 4 h post		
Cleansing including at least 2h soaking)	X	#							
Fluid balance ⁹	X	X		X	X				
Randomization	X			Post S	Pre &Post				
Local lab Wound culture	X		4h Post R	4 h Post					
Local lab Blood culture	X								
12-Lead ECG (if feasible)		60, 40, 20 min pre treatment	During: 0.5, 2, 4h from start of first application only		During: 0.5, 2, 4h from start of first treatment only		12, 24, 48h	week 1	

⁸Clinical assessments will include % TBSA per depth, % eschar removed, % excised, % autografted, % wound epithelialization (TW and donor site, if relevant), % graft take as relevant.

⁹ Daily fluid balance will be monitored for 7 days from injury or until hospital discharge, whichever comes first for patients with catheter.

Statistical Analysis Plan V02 of 15 May 2018

Competence Center for Clinical Trials Bremen

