7.3.2.2. Secondary target variables

The following secondary endpoints will be evaluated in this study:

Reduction in surgical needs

Reduction of surgical need for excisional eschar removal is measured by an analysis of incidence of surgical eschar removal (tangential/ minor/ avulsion/ Versajet and/or dermabrasion excision).

Earlier eschar removal

The time when complete eschar removal has been achieved will be assessed for each patient on the entire eschar removal period. For definition of complete eschar removal, see Appendix 13.1.1.

Blood loss

Blood loss incurred during the eschar removal procedures will be evaluated. Actual blood loss will be measured by considering the estimated blood loss, changes in Hemoglobin during the eschar removal procedures and the amount of units of blood transfused. Blood loss (Actual Blood Loss, ABL) will be calculated using the following formula [25]:

$$ABL = \frac{EBV * (Hb_{before} - Hb_{after})}{(Hb_{before} + Hb_{after})/2} + V_{WB} + \frac{5}{3} V_{PC}$$

EBV= Estimated blood volume is assumed 70 cm³/Kg

(Hb_{before}- Hb_{after})= Changes in Hb following each eschar removal procedure

V_{WB}= Volume [mL] of whole blood transfused

V_{PC}= Volume [mL] of packed red blood cells transfused.

The ABL will be summed over all procedures carried out to remove eschar, with the Hb measured immediately before each procedure and 4 hours after its completion. The amount of blood transfused will be summed over all transfusions carried out during all debridement procedures and 4 hrs later i.e. the before-after periods that are spanned by these Hb measurements.

Additionally, ABL will also be computed using the formula above, but over the whole eschar removal period (not procedure wise) i.e. the eschar removal process will be considered as one continuous procedure. Therefore, only the Hemoglobin value before the first eschar removal procedure and after the last procedure will be used and all blood transfusions performed between these measurements will be included.

Analyses with both blood loss values will be conducted. However, some missing values are expected. The analysis with less missing values will be regarded as more reliable and is therefore considered the main analysis. The other analysis is considered supportive.

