Serum chemistry, hematology and urinalysis testing will be performed at a central laboratory during the eschar removal phase. Any additional procedures during the wound management phase require hematology tests, as described in the protocol, and will be performed using Central lab. Pregnancy testing, HbA1c, leukocyte count (at Screening, in addition to central lab hematology), wound cultures, blood cultures, PTT/INR and biopsies will be performed locally on-site.

The following tests are performed in special laboratories: Pharmacokinetics test, Immunogenicity evaluation and evaluation of QT prolongation (using multiple ECG tests).

Serum Chemistry:

Urea, Creatinine, Glucose, Total Bilirubin, Cholesterol, Triglycerides, Uric Acid, Total Protein, Albumin, Globulin, Calcium (Ca++), Phosphorous, Sodium (Na+), Potassium (K+), Chloride (Cl-), Alkaline Phosphatase, SGOT (ASAT), SGPT (ALAT), LDH.

Hematology:

Hemoglobin, Hematocrit, RBC, MCV, MCH, MCHC, Platelets, Leukocyte count (WBC) with differential count (absolute numbers).

HbA_{1c} will be assessed at a local lab at Screening for diabetic patients as captured during the medical history.

PTT and INR will be tested at a local lab pre treatment and 4 hours after start of eschar removal.

Pregnancy Testing:

A serum pregnancy (β HCG) will be performed at a local lab for women of child bearing potential.

Urinalysis:

pH, Ketone, Specific gravity, Protein, Glucose, Bilirubin, Microscopic examination.

Qualitative Wound Culture:

Test burn wound for microbial flora (swab).

Blood Culture:

Test blood for microbial flora.

Diagnosis of Invasive Burn Wound Infection is based on Quantitative (Histological) Wound Culture Biopsy:

Infection should be assessed clinically by symptoms and signs that include local burn wound signs purulent drainage, erythema, warmth, exudation, odor, pain, and systemic signs that may or may not be related to the burn wound, such as fever, and leukocytosis as well as wound size and time to wound healing. Histological Biopsy may be performed to rule out suspicion of a clinical invasive burn wound infection (please refer to Appendix 8- Biopsy & Histologic Assessment Method) [26].

Clinical Invasive Burn Wound Infection will be defined when an Invasive Burn Wound Infection is diagnosed by quantitative bacterial count of $>10^5$ organisms per gram of tissue and histological signs of bacterial invasion of healthy tissues will define a positive invasive burn

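### Blood loss is counted only to the end of eschar removal, so graft bleeding at an excision is included and later graft bleeding is not; this can give NexoBrid a net advantage in the fourth confirmatory test

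*SAP*

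**What the plan says.** SAP section 7.3.2.2 sets the scope of the secondary endpoint: "Blood loss incurred during the eschar removal procedures will be evaluated". Section 10.3.3.3.1 gives two versions.

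- Per procedure: "The ABL will be summed over all procedures carried out to remove eschar, with the Hb measured immediately before each procedure" and again 4 hours after it ends.
- Continuous: one interval for the whole process, "pre first procedure to 4 hrs post last procedure (in which complete debridement was achieved".

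The version with fewer missing values becomes the main analysis. Section 11.1.8 places blood loss fourth in the testing hierarchy.

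On grafting, section 2.1 describes surgical removal as usually tangential excision with split-thickness autografting, and adds: "The surgically excised raw wound bed should be covered immediately, i.e., in most cases autografted". Footnote 4 to Table 1 (section 7.2) puts later operations under wound management, which covers "post complete eschar removal additional excisions, Autografts, and donor site data if relevant". Section 7.3.3.5 says: "Any additional procedures during the wound management phase require hematology tests, as described in the protocol".

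The second objective in section 2.2 concerns reduction in "surgical burden and its related blood loss as compared to SOC". The background in section 2.1 lists less blood loss through fewer excision and autografting operations as an indirect benefit of NexoBrid.

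**The concern.** The Hb interval around an excision runs from just before the procedure to 4 hours after it. If the bed is grafted in that session, bleeding from donor harvest and grafting lies inside the interval, and the SAP has no rule to separate it. If the same wound is cleared by a topical agent or by dressings and grafted some days later, that bleeding falls outside both ABL versions.

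Whether graft bleeding counts therefore depends on whether eschar was removed by excision, and excision is expected to be much commoner in SOC. Part of a difference in test 4 could come from where the window ends rather than from less bleeding. That matters because the objective speaks of the blood loss that goes with the surgical burden.

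**Working it through.** **1. The SAP's excision rates.** Section 9.2 anticipates excision in 0.24 (NexoBrid) and 0.60 (SOC), with 43 per arm for 90% power by Fisher's exact test at two-sided 5%. Exact enumeration at 43 and 43 gives power 0.904, so the figure reproduces.

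**2. Who can have excision-session graft bleeding counted.** With 75 per arm (section 9.3.1):

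- SOC: 0.60 × 75 = 45 patients
- NexoBrid: 0.24 × 75 = 18 patients
- Difference: 0.60 − 0.24 = 0.36, or 27 patients

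These are upper limits, since not every excision is grafted in the same session.

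**3. What one graft operation contributes.** The SAP formula without transfusion is ABL = EBV × (Hb before − Hb after) / mean Hb. At an assumed 70 kg, EBV = 70 × 70 = 4900 mL. For assumed falls from 13 g/dL:

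- to 12.5: 4900 × 0.5 / 12.75 = 192 mL
- to 12: 4900 × 1 / 12.5 = 392 mL
- to 11: 4900 × 2 / 12 = 817 mL

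**4. Net difference from the window alone.** Assume that total graft bleeding is equal in the two arms, and that a share q of excised patients is grafted in the same session, with the same q in each arm. The net difference against SOC is 0.36 × q × g, where g is bleeding per graft. For q from 0.5 to 1.0:

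- g = 192 mL: 35 to 69 mL
- g = 392 mL: 71 to 141 mL
- g = 817 mL: 147 to 294 mL

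**5. Effect on the test.** The SAP gives no SD for blood loss, so g must be expressed in assumed SD units. The standardised difference is 0.36 × q × g/SD. The last column is the chance of two-sided significance with 75 per arm, on a comparison of means.

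| q | g/SD | Difference (SD) | Chance of significance |
|---|---|---|---|
| 0.5 | 0.5 | 0.09 | 8% |
| 0.5 | 1.0 | 0.18 | 20% |
| 1.0 | 0.5 | 0.18 | 20% |
| 1.0 | 1.0 | 0.36 | 60% |
| 1.0 | 1.5 | 0.54 | 91% |

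The span shows that the effect could be anything from negligible to decisive. It does not estimate the effect.

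**6. Whether another planned analysis covers this.**

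- The hematocrit and hemoglobin versions (11.1.5.6, 11.1.5.7) use debridement procedures only.
- The comparison of NexoBrid with surgical procedures (11.1.5.8) uses the same per-procedure ABL.
- The early- and late-graft subgroups (11.1.5.9) omit blood loss.
- Transfused volume (11.1.4.11) does extend past eschar removal, but it misses bleeding that was not transfused.

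**The case against.** The strongest reply is that the endpoint is openly limited to eschar removal. Section 7.1 says that the arms differ only at that stage, so measuring blood loss there is a coherent choice, and the objective can be read the same way. This stands: the formula contains no error and the endpoint need not be replaced.

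A reader might infer that graft bleeding is charged to SOC and left out for NexoBrid. The SAP does not support that. The rule follows the procedure. On the planning rates, about 24% of NexoBrid patients have an excision and are charged for any graft in that session. About 40% of SOC patients have none, and their later grafts are excluded too. Nor is later grafting never counted: in the continuous version, if one wound is grafted while another still carries eschar, that bleeding falls inside the window in either arm.

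Three further points stand in part.

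- That excision and grafting share one Hb interval is inferred from background text. It is not stated as a procedure of this trial.
- Section 2.1 says that excision sacrifices healthy dermis and so usually makes grafting necessary. Some graft bleeding counted in SOC is therefore a real consequence of the removal method.
- Donor-site number and area (11.1.5.4, 11.1.5.5), graft counts and repeat grafting (11.1.5.9) and transfusion by period would help show whether grafting was deferred. None of them measures blood loss on an Hb basis.

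**Conclusion.** The concern holds as a net asymmetry. Both ABL versions end with eschar removal, excision is expected 36 percentage points more often in SOC, and no Hb-based analysis follows grafting done afterwards. A NexoBrid advantage in test 4 could therefore partly reflect deferred graft bleeding.

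The size cannot be derived from the SAP. The figures in steps 3 to 5 rest on assumed body weight, Hb falls, same-session grafting, SD units and equal total graft bleeding. If NexoBrid patients are truly grafted less, the artefact is smaller.

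It is tempting to multiply the per-graft loss by an assumed 20% to 50% of NexoBrid patients grafted later, which gives 38 mL (0.20 × 192) to 408 mL (0.50 × 817) omitted per NexoBrid patient on average. That is not a bias estimate, because nothing is subtracted for SOC patients grafted after non-surgical debridement.

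**What to change.** Keep the endpoint and its place in the hierarchy, and make these changes.

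1. In 10.3.3.3.1 and 11.1.3.3, add a prespecified supportive comparison of NexoBrid with SOC. It sums procedure-wise ABL over all eschar-removal procedures and all wound-management surgery on target wounds, including further excision, autografting and donor harvest, until wound closure.
2. In 10.1.1.3, extend the imputation model to those procedures, for example with a procedure-type level for grafting and with graft and donor area as covariates. The present model distinguishes only surgical from non-surgical procedures.
3. Tabulate by arm how many eschar-removal procedures included grafting in the same session.
4. State that a claim of reduced blood loss refers to the eschar-removal period only, unless the extended analysis agrees.

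The hematology is already required, so the cost is SAP text, one more analysis and a longer imputation specification. The downsides are more procedures with possibly missing Hb and a figure that may be less favourable. If total surgical bleeding is truly lower with NexoBrid, the extended analysis would support the claim.
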